Process to provide incentives. Deposits to the participant's ClinCard will be made electronically through a University of Pennsylvania-approved partnership with Greenphire. Greenphire's ClinCard program is HIPAA-certified. Social security numbers, names, addresses, and date of birth for all persons to whom incentive payments are sent are kept within the ClinCard system. Each year, Accounts Payable at the University of Pennsylvania securely downloads a report from Greenphire that includes anyone paid in the previous calendar year. That data is kept secure and only the data of people that earned \$600 or more is uploaded to a secure third party vendor to process 1099's.

Transfer of body weight data for assessments. Participants will measure their body weight using a digital scale in their home that the study will have shipped to them. Upon receipt of the scale, participants will receive instructions on how to weigh themselves, take a photo of their weight on the display, and submit the photo to the study by texting the photo to the study's number in the Way to Health system.

Transfer of prescription fill data. Each month, study staff will upload to MiShare a file containing the prescription drug plan ID numbers of all current study participants. A member of the University of Michigan's Prescription Drug Plan team will run a query, based on the prescription drug plan ID provided, for the claims extract of the metformin claims for the previous month for study participants only. The results will be uploaded to MiShare to share with select study staff, and study staff person will download and store the data in the study folder.

Transfer of Diabetes Prevention Program participation and body weight data. All study participants will be encouraged to enroll in Omada Health's online DPP. Participants will be directed to a special URL set up only for BEST Change participants, and this special URL will allow Omada to share monthly reports with study staff containing data only on study participants. Data to be shared on each study subject also enrolled in the Omada program: number of lessons completed, days body weight measured, days physical activity is tracked, and days meals or snacks are tracked. body weight at start of the DPP, percent weight lost each week, and dates when participant has lost 5% and 10% of their body weight. The monthly reports will be shared using the secure SFTP site GoAnywhere, and only select study staff will have access to the files. An authorized study staff person will download and store the data in the study folder. A data sharing agreement between UM and Omada Health is in progress.

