Overview. To test our novel strategy of linking financial incentives and preventing T2DM to people's roles, values, and strengths, our team of experts in T2DM prevention, behavioral economics, and SDT will conduct a 4-arm pragmatic RCT among patients of Michigan Medicine (the U-M health system) who have prediabetes and U-M Premier Care health insurance. Our study will utilize the Way to Health (W2H) web platform of the University of Pennsylvania (Penn). This platform was developed with support from NIH and permits automated delivery and efficient evaluation of behavioral interventions that leverage insights from behavioral economics. We will compare the effects of 12 months of (a) financial incentives plus tailored messages based on SDT principles, (b) financial incentives alone, (c) tailored messages based on SDT principles alone, and (d) an enhanced control group on the primary outcome of change in HbA1c. These four arms will enable evaluations of the effects of adding tailored messages to financial incentives (i.e., financial incentives plus tailored messages vs. financial incentives alone), adding financial incentives to tailored messages (i.e., financial incentives plus tailored messages vs. tailored messages alone), and adding both tailored messages and financial incentives to automated feedback (i.e., financial incentives plus tailored messages vs. enhanced control). To measure the primary outcome of change in HbA1c, and secondary outcome of change in weight, we will conduct assessments at baseline, 6, and 12 months. To measure the secondary outcome of participation in a DPP or use of metformin we will use health insurance claims data. We will measure mediators and moderators of intervention effectiveness by surveying participants at baseline, 6, and 12 months. To identify facilitators of and barriers to intervention implementation and sustainability, after the 12-month intervention we will interview participants, workplace health promotion staff, and PCPs. We will then conduct a comprehensive evaluation of program implementation and sustainability using the Reach, Effectiveness, Adoption, Implementation, and Maintenance (RE-AIM) and Consolidated Framework for Implementation Research (CFIR) frameworks.

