Our pilot study's primary outcome was change in autonomous motivation for weight loss as measured from six to 42 by the Treatment Self-Regulation Questionnaire (TSRQ). While high baseline levels of autonomous motivation (mean 37.6 with 18 participants scoring 42) limited our ability to detect intervention effects on autonomous motivation, the eight intervention participants with a baseline autonomous motivation score less than 35 had a mean 4.4 point increase (95% CI, -1.4 to 10.1) in autonomous motivation after 12 weeks. The 31 intervention participants lost an average of 3.6 pounds (95% CI, -5.6 to -1.4), and using 0 to ten scales reported high median ratings for intervention acceptability (8), satisfaction (8), and willingness to repeat (10). Participants completed 95% of the week 12 weight measurements and 98% of the week 12 and 24 surveys. In 20 post-intervention interviews, 80% of participants said they would participate in a similar study for up to 24 months. These findings demonstrate the approach's high acceptability, the feasibility of our recruitment and tracking mechanisms, and preliminary efficacy of the Financial Incentives Plus Tailored Messages intervention.

Methodology

Inclusion and Exclusion Criteria

Inclusion Criteria	Source
Primary Care Provider part of Michigan Medicine	

BMI of 25 or higher (23 or higher if of Asian descent)	Custom Pull from MM medical records, Data Office for Clinical and Translational Research (DOCT-R), UM School of Medicine and confirmed in screener questionnaire
Age 18 or older	
Primary health insurance is U-M Premier Care, Community Blue PPO by BCBSM, or Comprehensive Major Medical by BCBSM	Custom Pull from MM medical records, DOCT-R and asked if primary screener questionnaire
Recent Hgb A1c 5.7 – 6.4% (inclusive)	Custom Pull from MM medical records, DOCT-R and confirmed during screening process via blood test at MLab
Exclusion Criteria	Source
Expects to change health insurance plan in the next three months to something other than the three listed above	Online screener questionnaire in Way to Health (W2H) or screened over the phone by study staff; entered into Qualtrics
Is enrolled in Medicare or plans to enroll in Medicare in the next 12 months	Online screener questionnaire in Way to Health (W2H) or screened over the phone by study staff; entered into Qualtrics
Participated in pretesting of intervention materials	List of 10-30 pretesters kept by study staff

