Ever diagnosed with T2DM as indicated by the following ICD codes: 
 • E08 Diabetes mellitus due to underlying condition • E09 Drug or chemical induced diabetes mellitus • E10 Type 1 diabetes mellitus • E11 Type 2 diabetes mellitus • E13 Other specified diabetes mellitus • 250 Diabetes mellitus (ICD-9) 	Custom Pull from MM medical records, DOCT-R and confirmed in screener questionnaire
Serious mental health conditions as indicated by the following ICD-10 codes: 
 F20 Schizophrenia F21 Schizotypal disorder F22 Delusional disorders F24 Shared psychotic disorder F25 Schizoaffective disorders F28 Other psychotic disorder not due to a substance or known physiological condition F29 Unspecified psychosis not due to a substance or known physiological condition F31 Bipolar disorder F33.2 Major depressive disorder, recurrent severe without psychotic features 	Custom Pull from MM medical records, DOCT-R

F33.3 Major depressive disorder, recurrent, severe with psychotic symptoms	

End-stage renal disease is indicated by the following ICD codes:
 
N18.6 End stage renal disease Z99.2 Dependence on renal dialysis ICD-9-CM 585.6 End stage renal disease ICD-9-CM V45.11 Renal dialysis status
	Custom Pull from MM medical records, DOCT-R
Alcohol dependence (ICD-10: F10.2) and opioid dependence (ICD-10: F11.2)	Custom Pull from MM medical records, DOCT-R
Unable to send and receive several text messages weekly	Online screener questionnaire in Way to Health (W2H) or screened over the phone by study staff; entered into Qualtrics
Does not have a smart phone	
Currently taking metformin	
Unable to take metformin due to contraindications or side effects	
Participated in a Diabetes Prevention Program covered by UM Premier Care insurance	
Currently enrolled in an interventional research study that is examining how a diet, program, or drug might: promote physical exercise, healthy eating habits, or weight loss; lower blood pressure; or lower blood sugar	
Not planning to live in local area over the next year	
Pregnant or planning a pregnancy in the next year	
Received treatment for an eating disorder (e.g. anorexia or bulimia), not including binge-eating disorder, in last 12 months	
Intensive cancer treatment such as bone marrow transplant, chemotherapy, radiation, or cancer related surgery (not including hormonal chemotherapy like Tamoxifen) in last six months or near future	

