Organ transplant in last six months	
Bariatric/ gastric bypass surgery, gastric sleeve surgery, or gastric balloon procedure in last six months	

Stroke, heart attack, heart surgery, or hospitalization for congestive heart failure in the past three months	
Other serious health issues or personal concerns that could prevent participant from completing study	

Patients of Michigan Medicine with U-M Premier Care health insurance (either because they are U-M employees or dependents of U-M employees) will be eligible to participate. The U-M has nearly 50,000 diverse employees (25% minority and 60% female) across three campuses. Nearly 75% of U-M employees with U-M health insurance choose Premier Care for their coverage.

Premier Care currently covers the online DPP offered by the company Omada at no cost to plan members with prediabetes. Premier Care also covers metformin as a Tier one (i.e., lowest co-pay) medication.

Recruitment

We will recruit 380 adults meeting the criteria in Table 1. Because the criterion of a certain A1c value range is verified after a participant is consented, we may need to enroll up to 500, with up to 120 being screen failures due to their baseline A1c value being outside of the prediabetes range. We will closely monitor recruitment and adjust our approaches if needed (with IRB amendment approval) to ensure we successfully reach our recruitment targets.

We conservatively estimate that at least 10,000 of the ~33,000 Michigan Medicine patients with U-M Premier Care insurance will meet these criteria. Patients will need to have one of the three insurance plans listed in Table 1 above to ensure coverage of the DPP and low cost-sharing for metformin. Exclusion criteria will include conditions that would make participation in a program to prevent T2DM unfeasible (e.g., inability to consent or illiteracy), inapplicable (e.g., prior diagnosis of T2DM, does not meet an eligibility requirement of the online DPP) or potentially unsafe (e.g., alcohol or opioid dependence, serious psychiatric diagnoses, intensive cancer treatment).

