Mean 12-month change in HbA1c (defined as the 12-month measure minus the baseline measure) will be reported by arm. To test H1a and H1b, we will use an OLS regression model with 12-month change in HbA1c as the response variable. This model will include an indicator for each of the three arms (with the Financial Incentives Plus Tailored Messages Arm as the reference), stratification factors, baseline HbA1c values, and any baseline measures that are predictive of missing 12-month data. We will use similar, separate OLS regression models to predict our secondary outcomes of 12-month changes in weight (defined as the difference between the 12-month and baseline measures) and mean number of months (calculated out of 12 months to account for those who drop out before 12 months) in which individuals were engaged in a DPP, mean months in which individuals had a metformin PDC of at least 0.8, and mean months in which individuals were engaged in a DPP or had a metformin PDC of at least 0.8.

In alternate analyses, we will fit separate mixed-effects models for the primary and secondary outcomes using baseline, 6, and 12-month data as response variables and with time, study arm indicators, and interactions between time and study arm indicators as predictors and participants as random intercepts. We expect the changes in outcomes in intervention arms to be gradual over time and anticipate these longitudinal data models will confirm findings from our primary analytic approach to testing H1a and H1b, but if the findings differ, we will examine the source of any differences. For models for months of engagement in a DPP or use of metformin, we will first assess the distribution for skewness and, if more appropriate, a count data model (e.g., zero-inflated negative binomial) will be used instead of OLS.

Aim 2: Identify mediators and moderators of the effectiveness of financial incentives plus tailored messages based on SDT principles, financial incentives, and tailored messages based on SDT principles.

H2a: Combo Arm on 12-month change in HbA1c will be mediated by changes in autonomous motivation and changes in controlled motivation.

H2b: Effects of the Financial Incentives Arm on 12-month change in HbA1c will be mediated by changes in controlled motivation.

H2c: Effects of the Tailored Messages Arm on 12-month change in HbA1c will be mediated by changes in autonomous motivation.

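### The insurance-change exclusion looks ahead three months although plan coverage is needed for 12, and no rule says how metformin months after loss of drug-plan coverage are scored

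*Combined protocol and SAP*

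**What the plan says.** The exclusion list under Inclusion and Exclusion Criteria removes a patient who "Expects to change health insurance plan in the next three months to something other than the three listed above". Two neighbouring items use a year: a patient is excluded who "Is enrolled in Medicare or plans to enroll in Medicare in the next 12 months", or who is "Not planning to live in local area over the next year". The pregnancy criterion also covers the next year.

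The Recruitment section gives the reason for the insurance requirement: patients need "one of the three insurance plans listed in Table 1 above to ensure coverage of the DPP and low cost-sharing for metformin". The intervention lasts 12 months (Approach, Overview), and monthly incentives can be earned in 11 of them (Interventions, Financial Incentives Arm).

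Metformin fills reach the study through the U-M Prescription Drug Plan team, which "will run a query, based on the prescription drug plan ID provided, for the claims extract of the metformin claims for the previous month" (Transfer of prescription fill data). The Overview says in general terms that engagement comes from claims, but Measures and Data Collection takes DPP engagement from Omada's own reports. Under Analysis Plans, Aim 1, the engaged-months outcomes are "calculated out of 12 months to account for those who drop out before 12 months", and all outcome analyses are intent-to-treat. The plan does not say how a month without coverage is scored, does not track coverage during follow-up, and has no sensitivity analysis for it.

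**The concern.** The criterion protects access for a quarter of the period in which access is needed. A patient who already expects to join another employer's or a spouse's plan in month 4, stays in the area and is not approaching Medicare passes every listed criterion.

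What is at stake is mainly measurement. If that patient's fills move to another drug plan, the monthly query returns nothing. With a fixed denominator, an unseen fill becomes a month of non-adherence. Such a month does not look missing, so it would not count toward the trigger of more than 10% missing 12-month data that starts multiple imputation. The same fill data feed the monthly feedback messages and the incentive payments, so an adherent leaver could be told that they were not engaged.

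**Working it through.** **1. Look-ahead against need.** The insurance look-ahead is 3 months and the intervention is 12, so 12 - 3 = 9 months are not covered by the question. The window runs from screening, which precedes consent, the A1c test, the baseline survey and randomisation. No later step asks again about an expected plan change.

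**2. The plan's own power.** Inputs from Sample Size: 85 per arm, α = 0.017, difference 0.2% and SD 0.4% for H1b, so d = 0.2/0.4 = 0.5. Two-sided testing is assumed because the plan does not state it.
- Normal approximation: √(85/2) × 0.5 - 2.387 = 0.873, giving power of 80.9%. The t-based value is 80.1%. The stated 80% reproduces.
- For H1a (d = 1.0), power exceeds 99.99%, consistent with the stated 99%.
- Enrolment: 85/0.9 rounds up to 95 per arm, and 95 × 4 = 380, as stated.
- The plan also names d = 0.5 as the detectable effect for the secondary outcomes, so 80.1% is the baseline for step 4.

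**3. Months lost by a leaver.** If leaving is spread evenly over the starts of months 4 to 12, the covered months are 3, 4, ..., 11, with mean 63/9 = 7. The mean loss is 5 of 12 (41.7%). If everyone leaves at the start of month 4, the loss is 9 of 12 (75%).

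**4. Dilution of the engagement contrast.** Let f be the share leaving, equal across arms, and L the share of months lost. If every later month scores zero and the between-arm difference accrues evenly over the year, it shrinks by f × L. The documents give no value for f, so a range is shown. Power is t-based for d = 0.5 × (1 - fL), with the SD unchanged.

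| f (assumed) | Shrinkage, even leaving | Power | Shrinkage, all at month 4 | Power |
|---|---|---|---|---|
| 2% | 0.8% | 79.3% | 1.5% | 78.7% |
| 5% | 2.1% | 78.2% | 3.8% | 76.6% |
| 10% | 4.2% | 76.1% | 7.5% | 72.7% |
| 20% | 8.3% | 71.8% | 15% | 64.1% |

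In absolute terms, 0.05 × 5 = 0.25 and 0.10 × 5 = 0.5 observable months are lost per participant. The loss in engaged months is smaller, because a month without engagement scores zero anyway. If the difference accrues only over months 2 to 12, L becomes 5/11 and 10% leaving gives 4.5%, so the result is not sensitive to that choice.

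**5. Which outcomes depend on coverage.**
- *HbA1c and weight:* a Michigan Medicine lab test and a photograph of a home scale. Neither depends on claims.
- *DPP months:* Omada reports through a study-specific link. They are affected only if Omada access ends.
- *Metformin months:* the drug-plan query. They are affected if drug-plan coverage ends.
- *Combined months:* a month with DPP engagement still counts. Only months without it are in doubt.

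**The case against.** The strongest reply is that nothing in the documents shows a plan change ending what the study can see. The drug plan is identified by its own member number, and no section says that leaving a listed medical plan ends it. Omada reports directly. This stands, and it makes the scoring problem conditional.

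A reader might infer that the intervention cannot act, and the outcome cannot be observed, for up to nine months. The documents do not support that. Text messages do not depend on insurance, the Background says that a growing number of private insurers cover the DPP, and HbA1c and weight are collected regardless. An effect on HbA1c would have to come through lost access to the DPP or metformin, and there is no figure for that. Nor is it a defect of this criterion that a leaver's incentive share passes to others, since that is the stated rule for every non-earner.

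The Medicare and residence criteria already remove two groups of foreseeable leavers. The catch-all item, "Other serious health issues or personal concerns that could prevent participant from completing study", might remove a few more, although it does not mention insurance. A screening question cannot catch unexpected changes. A month in which someone really stops after leaving is a true zero and belongs in an intent-to-treat result. All of this limits the size of the problem.

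Finally, Aim 4 was added after the primary and secondary outcomes had been analysed, so a wording change comes too late for the participants in that analysis. That also stands. It does not answer the missing scoring rule, which can still be examined.

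**Conclusion.** The mismatch is in the text and is unexplained: a three-month look-ahead for coverage needed over 12 months, beside criteria that look ahead a year. The consequence for the outcomes is conditional and probably small. Metformin months are wrongly scored as zero only if a leaver's drug-plan coverage ends and they keep filling elsewhere.

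If 5-10% leave evenly over months 4 to 12 and all later months score zero, the engagement difference shrinks by at most about 2-4%, and power for d = 0.5 falls from 80.1% to 78.2-76.1%. Early leaving would roughly double the shrinkage. These rates are assumptions and include unforeseen leavers, so a 12-month question would recover only part of the loss. With randomised arms the expected effect is dilution; bias between arms would need leaving to differ by arm. The concern rests on the secondary metformin and combined engagement outcomes, and on the DPP outcome only if Omada access ends. It gives no ground for doubting the HbA1c measurements.

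**What to change.** **Further enrolment or reuse of the protocol.** Extend the insurance look-ahead to 12 months, or explain why three is enough. The cost is a change to the screener wording and slightly more screen failures, limited to people who already expect to leave. The Recruitment section estimates at least 10,000 eligible patients for 380 places, so this is easily borne.

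**Participants already enrolled.**
- Obtain each participant's coverage end date from the Prescription Drug Plan team, and report the number leaving by arm. This replaces the assumed rate with an observed one.
- Keep the out-of-12 result. Beside it, report a sensitivity analysis that treats metformin months after loss of coverage as unobserved. For the combined outcome, count such a month as engaged if Omada shows engagement, and otherwise as unobserved.
- Establish whether a plan change ended Omada access, and state how DPP months were scored in that case.
- State the three-month window as a limitation, and label the sensitivity analysis post hoc.

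The cost is one field from an existing data provider and one additional analysis. Leaving happens after randomisation, so the covered-months result needs its own caution if leaving differs by arm. That is a reason to report it alongside the out-of-12 result and not in its place.

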Aim 3: Evaluate facilitators of and barriers to scalability, acceptability, and sustainability of financial incentives plus tailored messages based on SDT principles, financial incentives, and tailored messages based on SDT principles. To identify facilitators of and barriers to intervention implementation and sustainability, we will interview participants, workplace health promotion staff, and health system staff. With these interview data and program cost data, we will evaluate program implementation and sustainability using an integration of the Reach, Effectiveness, Adoption, Implementation, and Maintenance and Consolidated Framework for Implementation Research frameworks.

Aim 4: Compare 12-month changes in HbA1c and weight in the Enhanced Usual Care (EUC) arm to similar patients who received no intervention. This exploratory aim was added after analyses of primary and secondary outcomes found that participants in the least research-intensive arm, the Enhanced Usual Care (EUC) arm, saw the best improvements in weight and HbA1c. We will conduct an analysis to compare the HbA1c and weight outcomes in the EUC arm to similar patients who received no intervention (external controls). The results will be used to provide context to staff who we interview as part of Aim 3.

Background Information

Significance

Prediabetes Is a Major Public Health Problem in the United States. Prediabetes is an asymptomatic condition in which patients' blood glucose levels are higher than normal but not high enough to meet diagnostic criteria for type 2 diabetes mellitus (T2DM). The American Diabetes Association (ADA) defines prediabetes as either a fasting plasma glucose (FPG) of 100 to 125 mg/dL, a 2-hour plasma glucose of 149 to 199 mg/dL after a 75-gram oral glucose tolerance test, or a hemoglobin A1c (HbA1c) of 5.7% to 6.4%. An estimated 84 million US adults have prediabetes, which is associated with an approximately 3-fold greater annual incidence of T2DM and an approximately 50% greater risk of consequent cardiovascular disease.

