Data pull and outreach. We will use queries of the Michigan Medicine electronic health record (EHR) to identify patients who meet the inclusion a subset of the criteria in Table 1. The A1c must have been completed at least 30 days ago and less than 12 months ago and have a value from 5.7% to 6.4%, inclusive, or not have had an A1c test in the last year. The list of patients will be reviewed to remove any patients who are not eligible because they participated in the pretesting of study intervention materials (10-30 patients). The remaining patients will be mailed (and/or emailed, when email is listed in health record) a two-sided 5x8 card, in a brightly colored envelope, that describes the study. To protect privacy, the envelope will have the University of Michigan Medical School name, return address, and the block "M," and in the bottom left corner, the text, "Chance to participate in a research study that could benefit you and your health!" On the recruitment card and email, recipients are given the chance to "opt-out" of any further communications about the study by emailing or calling the provided contact information. The email message will contain similar text and photographs as the mailed card, but exact layout will be modified to fit the communication mode.

Website on Qualtrics. The postcard and email direct them to a website hosted in Qualtrics that first asks if they received a mailed card or email about the study that was addressed to them. We ask this question because we anticipate some interested potential participants going to the website after hearing about the study from family and friends who we contact directly.

If they respond that they *did* receive a postcard or email addressed to them, they are taken to pages with more information about the study, contact information for study staff so potential participants can ask questions, and a question about their interest that, if answered affirmatively, takes them to the W2H platform so that they can begin the screening process.

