meaning. Good illustrative statements will be captured verbatim and indicated as such. Notes will be stored in a secure study folder on a departmental shared drive. Interview notes will be coded and analyzed using NVivo software. A code book will be developed beginning with the key domains from the interview guide and using an iterative process among three study staff and PI, with additional codes and subcodes added to account for details that emerged during interviews. The same four individuals will independently code four set of notes and will discuss concordance (Hemmler et al., 2022) to resolve discrepancies in coding via a consensus process. If the study team determines that a high level of consistency in coding had been established, then the sets of notes will be coded independently, with coders applying a “flag for review” code to any sections of text where the coder would like confirmation of a code via team review. If consistency in coding is not established after the group codes four sets of notes, more notes will be coded until consistency in coding is established. The codebook will be revised as needed to reflect new codes that emerge, with notes being recoded as needed. Once coding is complete, the four study team members will independently review key code reports and discuss interpretation of findings. Findings may be used to assist in interpreting study outcomes, improve the program itself, and to identify potential facilitators of and barriers to adoption, implementation, and sustainability. In reports and manuscripts, all data will be deidentified.

9. External controls data. Prior to conducting interviews with the key stakeholders described above as data source #7, we will obtain data that will allow us to share with those interviewed a comparison, between the EUC arm and similar patients who had no intervention, of changes in weight and HbA1c over approximately twelve months. Data will be of patients matching the same initial eligibility criteria that were used for the data pulls for recruitment. Patients will be excluded if they participated in the study, declined to participate after a recruitment call, were unable to reach for recruitment, or were ineligible as determined by screening. Variables provided will be: coded identifier, height, age, sex, race, ethnicity, and both weight and HbA1c with corresponding measurement dates.

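### Aim 4 selects external controls with the recruitment-pull criteria but does not say at which date those criteria are evaluated; if at the extract date, controls who progressed to diabetes drop out and comparable trial participants do not

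*Combined protocol and SAP*

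**What the plan says.** Specific Aims, Aim 4, gives the timing: "This exploratory aim was added after analyses of primary and secondary outcomes found" that the EUC arm (the Enhanced Control Arm elsewhere) had done best. The control data are therefore drawn after trial follow-up.

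Measures and Data Collection, item 9, defines the controls: "Data will be of patients matching the same initial eligibility criteria that were used for the data pulls for recruitment". It wants "changes in weight and HbA1c over approximately twelve months". The listed variables include dates for weight and HbA1c, but no diagnosis date and no pull or index date.

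The criteria themselves are worded relative to the pull:

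- **Diabetes.** The Inclusion and Exclusion Criteria table excludes patients "Ever diagnosed with T2DM as indicated by the following ICD codes" (E08 to E11, E13 and ICD-9 250). Its source is given as "Custom Pull from MM medical records, DOCT-R and confirmed in screener questionnaire", so it is one of the pull criteria.
- **HbA1c.** Under Recruitment, the data-pull paragraph says "The A1c must have been completed at least 30 days ago and less than 12 months ago", with a value of 5.7% to 6.4%, and offers a second route: "or not have had an A1c test in the last year".

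Analysis Plans, Aim 4, matches or adjusts for demographics and for baseline BMI, weight and HbA1c, and includes the interval between measurements as a covariate. The general paragraph of Analysis Plans applies intent-to-treat to all outcome analyses.

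**The concern.** In recruitment, a rule against any past diabetes code looks only backwards from entry and is harmless. In a retrospective extract, the same rule run on the extract date also looks across the control's follow-up year. It then selects controls on something that happens after baseline and is close to the outcome itself. EUC participants were screened once, at entry, and nothing removes them for diabetes coded later. The selection would act on one side only.

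The baseline covariates in the Aim 4 model cannot repair this, because the selection depends on what happened after baseline. Nor could the analyst see it in the data, since the variable list has no diagnosis date or pull date. The choice is in effect made when the data request is written.

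At stake is the message to the staff interviewed under Aim 3, who will be shown this comparison as context. A comparator without its progressors could suggest that the EUC programme adds less over no intervention than it does.

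**Working it through.** **The plan's own figure.** Aim 4 has no sample-size or precision calculation. The only design calculation is under Sample Size: 85 per arm, SD of change 0.4, difference 0.2, α 0.017 (two-sided assumed). SE = 0.4 × √(2/85) = 0.0614; 0.2/0.0614 = 3.26; 3.26 − 2.387 = 0.873, which gives power 80.9% (80.1% with the noncentral t) against the stated 80%. Inflation: 85/0.9 rounds up to 95, and 95 × 4 = 380. Both reproduce and neither is affected by this point. The SD of 0.4 and the 0.2 difference are used below as scale.

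**Effect of removing coded progressors.** If a proportion p of controls is removed and their mean change exceeds the mean of all controls by m, the control mean shifts by −p × m/(1 − p).

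Inputs from the protocol:
- SD of 12-month change 0.4
- mean change 0.0 without active treatment (the Enhanced Control Arm assumption)
- baseline range 5.7% to 6.4%, so 6.5% is the first value above it

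Assumptions, not in the protocol:
- baseline normal with underlying SD 0.2, truncated to that range, realised mean 5.88% to 6.09%
- change normal and independent of baseline
- 25%, 50% or 100% of those reaching 6.5% are coded with diabetes before the extract
- smaller change SDs of 0.2 and 0.3 as alternatives

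Simulation with 1,000,000 controls per scenario gives these shifts in control mean HbA1c change (points):

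| SD of change | Share crossing 6.5% | 25% coded | 50% coded | All coded | All coded, baseline-adjusted |
|---|---|---|---|---|---|
| 0.4 (protocol) | 9.0–20.5% | −0.016 to −0.027 | −0.032 to −0.058 | −0.066 to −0.131 | −0.069 to −0.140 |
| 0.3 (assumed) | 4.5–15.0% | −0.006 to −0.016 | −0.013 to −0.033 | −0.026 to −0.071 | −0.027 to −0.078 |
| 0.2 (assumed) | 1.4–8.7% | −0.001 to −0.006 | −0.002 to −0.013 | −0.005 to −0.027 | −0.005 to −0.030 |

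Check against the formula, for SD 0.4 and baseline mean 6.01. With all coded, p = 0.158 and the shift is −0.105, so m = 0.105 × 0.842/0.158 = 0.56. With half coded, p = 0.079 and the formula gives −0.079 × 0.56/0.921 = −0.048, which matches the simulated −0.048.

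Adjusting for baseline HbA1c does not remove the shift. On the scale of the 0.2 planning difference, the half-coded row at SD 0.4 is 0.032/0.2 = 16% to 0.058/0.2 = 29%.

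**The HbA1c window, counted back from the extract date.**

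- *Recent-test route, qualifying test as baseline.* The test is at most 364 days old, so follow-up cannot exceed 364/30.4375 = 11.96 months. If tests are spread evenly over the window (assumption), its width is 12 − 30/30.4375 = 11.01 months. The share with at least 11 months available is 1/11.01 = 9%, and with at least 9 months 3/11.01 = 27%.
- *Recent-test route, qualifying test as follow-up.* Twelve months is available, but the control outcome is then confined to 5.7% to 6.4%. At SD 0.4 this shifts the control mean by anything from −0.03 to +0.12, depending on the baseline mean.
- *No-recent-test route.* An older pair of tests 12 months apart is possible, but no rule says which value is baseline or that it must be in range.

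**With criteria fixed at each control's index date**, no control is removed for a later diagnosis, and this bias is zero by construction.

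**The case against.** The strongest reply is that item 9 may already mean the historical pulls. It speaks of initial criteria in the past tense. It then excludes people by what happened to them in recruitment (took part, refused, not reached, failed screening), which points towards the original lists. The Recruitment section describes the diabetes exclusion as "inapplicable (e.g., prior diagnosis of T2DM", and the Aim 4 analysis refers to baseline values for controls. On that reading no progressor is lost. This stands as a possible reading, and it is why the protocol cannot be said to remove progressors as written. It does not close the gap, because no date is stated and an analyst could run the criteria on either one.

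A reader might also infer that the HbA1c window leaves no 12-month follow-up at all. That goes too far. The recent-test route allows just under 12 months, the no-recent-test route allows older pairs, Aim 4 asks only for approximately twelve months, and the model adjusts for the interval.

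Nor do the documents support saying that the bias always runs against EUC or could reverse the result. A control coded and treated early in the year could have a lower HbA1c at follow-up, and reversal would need a true EUC advantage smaller than the shift. For insurance and BMI, neither direction nor size can be established.

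Finally, Aim 4 is exploratory, and a bias against EUC would not create a false benefit. That limits the stakes. It does not remove them, because the comparison is meant to estimate a difference that will be shown to stakeholders.

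**Conclusion.** The defect is a missing date, and it matters because one of the two available readings selects only the control group on a post-baseline event. Under that reading the control mean change would generally be too low and any EUC advantage understated. The amount is roughly 0.00 to 0.06 HbA1c points if up to half of those crossing 6.5% are coded, and up to about 0.13 if all are (0.14 after baseline adjustment). These sizes depend on the assumed baseline distribution, coding probability and, outside the 0.4 rows, SD of change. The protocol gives no incidence of diabetes and no target difference for Aim 4; the 0.2 used as a yardstick was set for the Combo Arm against the single-component arms. If the historical pull dates are meant, this bias is absent. The plan should be clarified before the extract is used. Aims 1 and 2 are not touched.

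**What to change.** In item 9 of Measures and Data Collection and in the Aim 4 analysis paragraph:

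1. Give each control an index date: either the baseline HbA1c date or the original recruitment-pull date.
2. Require an HbA1c of 5.7% to 6.4% at baseline, and state a window around 12 months for the follow-up value. These replace the recency window and the no-recent-test route for controls.
3. Evaluate every pull criterion (diabetes codes, other ICD exclusions, BMI, insurance) from records up to the index date only.
4. Keep controls who are later coded with diabetes, change coverage or move across the BMI limit.

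If the extract has already been drawn, report which date was used and redraw it if that was the extract date. Adding the index date and the date of any first diabetes code to the variable list would let the analyst confirm the rule was followed, but is optional.

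The cost is a revised data request and a few sentences of protocol text, with no patient contact.
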